**Objectives:**

The purpose of this research is to evaluate the effectiveness of two programs - Compassion Focused Program and Emotional Skills Training - on participants' emotional regulation, well-being, compassion, emotional skills, and anxiety-depressive symptoms compared to the control group in a subclinical population and clinical population

**Types of studies:**

- Multiple single-case study
- Randomized controlled study in subclinical population
- Pilot study in a clinical population

**Primary Objectives:**

Evaluation of the effectiveness of the Compassion Focused Program and Emotional Skills Training programs on participants' emotional regulation (DERS, Gratz & Roemer, 2004) compared to the control group.

**Secondary objectives and criteria:**

The secondary objectives are, in comparison to the control group, to evaluate (1) the effectiveness of the interventions on emotional regulation strategies (DERS, Dan-Glauser & Scherer, 2013), well-being (BE, Ryff, 1995, anxiety and stress symptoms (DASS21, Henry & Crawford, 2005), emotional competencies (S-PEC; Mikolajczak, Brasseur, & Fantini-Hauwel, 2014), and compassion (SCS; Neff, 2003) and (2) to assess program effectiveness processes on: feeling of effectiveness of emotional regulation (Bandura, 2006) and cognitive flexibility (CFI; Dennis & Vander Wal, 2010).

**Control variables:**

In addition to the primary and secondary objectives, we will control for two variables: participants' expectations of the intervention prior to the start of the program (QCA, Coste et al., 2019), and participants' satisfaction with the intervention at the end of the intervention (STTS-R, Oei & green, 2008).

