### Numbers of subjects to be included:

- Single case study: 10 participants, 5 participants per group
- Randomized controlled study: 123 participants: 41 participants per group
- Pilot study: 60 patients, 20 patients per group

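### Satisfaction measured at the end of the intervention is named as a variable to control for, although every objective is a comparison with the control group

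*Protocol*

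**What the plan says.** The Control variables section of the protocol states: "In addition to the primary and secondary objectives, we will control for two variables". The first is "participants' expectations of the intervention prior to the start of the program" (QCA). The second is "participants' satisfaction with the intervention at the end of the intervention" (STTS-R). The section names no outcome, model or arm.

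The objectives are all contrasts with control. The Objectives section sets the two programs "compared to the control group in a subclinical population and clinical population". Primary Objectives has the programs' effect on DERS "compared to the control group". Secondary objectives and criteria opens with "The secondary objectives are, in comparison to the control group, to evaluate".

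Numbers of subjects to be included gives "Randomized controlled study: 123 participants: 41 participants per group", a pilot of 60 patients with 20 per group, and "Single case study: 10 participants, 5 participants per group". The protocol does not describe what the control group receives, or whether it would rate satisfaction.

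**The concern.** A covariate in a randomised comparison should be fixed before randomisation, so that adjusting for it cannot remove or distort part of the treatment effect. Satisfaction at the end of a program fails that test. It can depend on which arm a participant was in and on how much the participant improved. If it is used as a covariate, the randomised comparison is affected in one of two ways:

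- **All arms give a rating.** The arm coefficient compares people with equal satisfaction, not the groups as randomised. It no longer answers the primary objective on DERS, nor the secondary ones.
- **Controls have nothing to rate.** The covariate is undefined in the control arm and the adjusted comparison cannot be fitted. No bias arises, but the sentence cannot be carried out.

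A lesser point concerns expectations. Collection before the program starts does not ensure collection before participants know their allocation, and expectations can shift once the allocation is known.

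**Working it through.** The protocol gives no figure to reproduce here: no effect size, SD, significance level or power. The group counts are consistent: 123/41 = 3 groups, 60/20 = 3 groups, 10/5 = 2 groups. The single-case study therefore shows no third, control group and is left out. The point concerns the randomised study. The same wording reaches the pilot, but how the pilot is allocated is not stated.

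**Controls have no rating.** A complete-case fit drops the 41 controls and leaves 123 − 41 = 82 participants. The model has four columns: intercept, two program indicators and satisfaction. Among the 82, the two indicators add up to the intercept, so the rank is 3 of 4 and the program-versus-control effect is not estimable.

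**All arms have a rating.** Only the 41 per arm comes from the protocol. All other inputs are assumptions:

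- one program against control, two-sided 5% test;
- outcome Y with within-arm SD 1, coded so that higher is better, and true effect d;
- satisfaction S with within-arm SD 1, differing between arms by g (program minus control);
- within-arm correlation rho between S and Y.

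The within-arm slope of Y on S is rho, so

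adjusted effect = difference in mean Y − slope × difference in mean S = d − rho × g.

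The standard error is approximately √[(1 − rho²) × (2/41 + g²/80)], where 80 = 2 × 40 is the within-arm sum of squares of S. For g = 0.5, rho = 0.3: √[0.91 × (0.0488 + 0.0031)] = 0.217. For g = 1, rho = 0.3: √[0.91 × (0.0488 + 0.0125)] = 0.236. Simulation (20,000 trials per setting) gave 0.218 and 0.237.

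| d | g | rho | d − rho × g | Significant benefit | Significant harm |
|---|---|---|---|---|---|
| 0.5 | 0.5 | 0.3 | 0.35 | 35.6% | 0.03% |
| 0.5 | 1 | 0.3 | 0.20 | 13.0% | 0.3% |
| 0.5 | 1 | 0.5 | 0.00 | 2.6% | 2.4% |
| 0.5 | −0.5 | 0.3 | 0.65 | 84.0% | 0.0% |
| 0 | 0.5 | 0.3 | −0.15 | 0.45% | 10.0% |
| 0 | 1 | 0.3 | −0.30 | 0.06% | 23.6% |
| 0 | −0.5 | 0.3 | +0.15 | 9.7% | 0.4% |

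The percentages are from the simulation. Without satisfaction in the model, the estimate at d = 0.5 is unbiased and power is 60.9% (exact noncentral t). At d = 0, each tail rejects at its nominal 2.5%. The bias is zero only if g = 0 or rho = 0.

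**The case against.** The strongest reply is that the protocol fixes no such analysis. The section names no model or outcome, and its opening clause sets the two variables beside the objectives, not inside them. The document seems to come from French (the schedule keeps some French words), and the French verb behind *control* often means check or verify. On that view, satisfaction is simply recorded. The heading and the verb would then trace to one translated word and would not be independent support for the covariate reading.

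Two further points are fair. The protocol attributes interventions to the two programs only, which fits controls without a rating better than controls with one; in that case no bias arises. And the numbers rest on assumed inputs: the pair g = 1, rho = 0.5 is exactly the one that cancels d = 0.5. They show a general property of post-treatment adjustment, not a prediction for this trial.

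What stands is that the monitoring reading is possible and that the harm is conditional. What does not stand is that the matter can be left to the SAP. The heading and the verb are the usual terms for adjustment, and the same verb governs pre-program expectations, an ordinary candidate covariate. Nothing limits satisfaction to a descriptive or within-program role. An SAP that followed the sentence as a covariate rule would inherit the problem; one that avoided it would depart from the protocol. Doubt about the meaning is itself a reason to reword.

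**Conclusion.** The concern holds and should be fixed, with medium confidence because it depends on the covariate reading. On that reading, the rule for the randomised study either changes what the program-versus-control coefficient estimates or cannot be carried out, and the protocol does not settle which.

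The actual size and sign of any bias cannot be determined from the protocol. Under the assumed values, the error can hide a benefit, suggest harm where there is no effect, or inflate a benefit. If monitoring was meant, the analysis is unaffected, but the sentence still needs rewording so that nobody follows it as a covariate rule.

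**What to change.** Reword the Control variables section as follows:

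- State that STTS-R satisfaction is not a covariate in any comparison with the control group. Report it descriptively, or as a labelled exploratory analysis within the two program arms.
- State that randomised comparisons are adjusted only for variables measured before randomisation, for example baseline scores.
- Allow QCA expectations as a covariate only if they are collected before participants know their allocation, and state that timing.
- If monitoring was what the section meant, say so.

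The cost is one or two sentences, with no extra participants or measures. The one operational consequence arises if QCA is to be a covariate: its collection must then come before allocation is known.

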**Inclusion criteria**

- Age between 18 and 65 years inclusive
- Person who can understand, speak and read French
- Person who was orally informed and gave informed consent to participate in the study
- Subject's participation in the study noted in the medical record

**Non-inclusion criteria**

- Participation in positive psychology, mindfulness or stress management groups for less than 3 months

## STUDY PROTOCOL

- Change in psychotropic medication (taking, stopping, or changing dosage) within 2 months prior to study participation
- Person with a mental disability
- Person deprived of liberty by court order

### Numbers of subjects to be included:

- Single case study: 10 participants, 5 participants per group
- Randomized controlled study: 123 participants: 41 participants per group
- Pilot study: 60 patients, 20 patients per group

### Provisional research schedule

SINGLE CASE STUDY	
Beginning of inclusions	November 2020
Inclusion period	1 months
Duration of interventions	3 months
Duration of participation for each subject	5 months
Exclusion period (=period during which the participant will not be able to participate in any other research involving an emotional regulation intervention)	5 months
RANDOMIZED CONTROLLED STUDY	
Beginning of inclusions	Février 2021
Inclusion period	18 mois
Duration of interventions	3 mois
Duration of participation for each subject	7 mois
Exclusion period (=period during which the participant will not be able to participate in any other research involving an emotional regulation intervention)	6 mois
PILOT STUDY	
Beginning of inclusions	August 2021
Inclusion period	2 months
Duration of interventions	3 mois
Duration of participation for each subject	7 months
Exclusion period (=period during which the participant will not be able to participate in any other research involving an emotional regulation intervention)	6 months
TOTAL RESEARCH TIME	31 months
END OF THE RESEARCH	March 2022

### **Benefits for participants**

The two interventions will allow individuals to become familiar with their emotions, to cope more easily with the emotional difficulties encountered in their daily lives and to develop new strategies to manage their emotions. Indeed, research shows that emotions contribute to an individual's ability to adapt to his environment by guiding him in social interactions (Keltner & Kring, 1998), by facilitating the detection of danger (Ohman et al., 2001), by preparing him to face a series of situations (Frijda, 1986), by accelerating and orienting his decision making (Bechara & Damasio, 2005) and by allowing him to memorize important elements more easily (Luminet & Curci, 2008). In this sense, the individual's skills in emotional regulation seem to be essential to his well-being.
